Cognitive performance will be measured by the C3B performance-based battery of cognitive tests at the end of the case. An overall score for a subject after a particular case will be calculated by first rescaling (e.g., so that each item ranges from 0 to 100) and then averaging the scores across the battery. Treatment effect will be assessed using a linear mixed effects model as described for Aims 1 and 2.

The significance level will be 0.05 for the primary outcome (Aim 1) and 0.05 across the 3 secondary outcomes (2 temperatures, cognitive function), such that the secondary outcomes will be assessed at a significance criterion of $0.05/3=0.017$. SAS statistical software version 9.4, Carey, NC, will be used for all analyses.

Specific Aim 4: Evaluate the difference between the surgeons' perceived ergonomic workload with and without a cooling vest during a prolonged and strenuous surgery.

Perceived ergonomic workload will be measured by duration of the surgical procedure recorded in minutes, surgeons' report of the number of hours slept prior to the study day, Borgs' visual analog scale for exertion (0-10), and the Rating of fatigue scale (0-10).

Perceived ergonomic workload for both conditions, with and without a cooling vest will be analyzed by descriptive statistics recommended for ordinal measured items – i.e., frequencies and median [quartiles].

We will use a linear mixed effects model to test the treatment effect of the cooling vest on mean perceived levels of exertion and fatigue. We will adjust for treatment, sequence and period effects, and include subject as a random effect to account for the within-subject correlation. We will test for differential carryover effect by assessing the treatment-by-period interaction. If no interaction is detected the interaction term will be removed and the treatment effect assessed in a main effects model.

Sample Size Justification.

Sample size calculation is based on having 90% power at the 0.05 significance level to detect a difference of 2 or more (on a scale of 0-10) on surgeons' self-rated thermal comfort with and without a cooling vest. With an estimate SD (s) of 3 for thermal comfort in each group, and an assumed within-subject correlation (ρ) of 0.5, the estimated SD of the within-subject difference would be

$$\sqrt{s_1^2 + s_2^2 - 2\rho s_1 s_2}, \text{ or } \sqrt{2(3^2) - 2(0.5)(3)(3)} = 3.$$

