Within these assumptions we would need a total of 26 subjects to have 90% power to detect a difference of 2 or more on mean thermal comfort in this crossover design. The detectable difference corresponds to an effect size (Cohen's D) of 0.66, which is medium to large. For the 3 secondary outcomes each using a significance criterion of $0.05/3=0.017$, we would have 90% power to detect an effect size of 0.76.

Our assumptions of variability and within-subject correlation for the primary aim will be reassessed in an internal pilot study after 13 subjects have completed the 4 cases, and the total sample reassessed based on the findings.

To ensure that sensors, iPad, and wireless technology can be monitored during a real-time surgical procedure, a small trial of two or three case studies will be conducted to ensure all processes work properly, which will not be included in the final data analysis. Periods of poor data or lead disconnection will be marked for exclusion in analysis.

Innovation

The discomfort surgeons experience during long surgical procedures combined with an inability to evaporate sweat through impervious surgical gowns prompted the innovative design of the disposable CoolSource™ Cooling System. The cooling vest is worn by surgeons under the impervious gown to reduce heat and improve comfort while performing surgery. The positive changes in mood, attention, and productivity have been reported by staff and surgeons in a product trial which supported the need for research to investigate the impact heat stress has in which supported the need for research to investigate the impact heat stress has in *real-time* operating conditions.

The **innovative** design of this study measures data by wireless sensor technology during *real-time* surgical procedures without disrupting the surgery, as previous studies utilized simulated conditions. Furthermore, limitations are numerous when trying to generalize findings discovered in structured simulated studies as there is a wider range of effecting factors in *real-time* investigations (Mazlomi et al., 2017). Information obtained from this study will support the development of prescriptive measures and standards to address heat stress in surgeons to alleviate perceptions of discomfort and improve physiological and psychological well-being.

Protection of Human Subjects

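### The fixed 0.05/3 criterion for the three secondary outcomes is valid, but Holm's step-down test keeps the same 0.05 familywise limit, is never less powerful, and takes one sentence to adopt

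*Combined protocol and SAP*

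**What the plan says.** The Data Analysis section, in the paragraph after Specific Aim 3, sets the error rates: "The significance level will be 0.05 for the primary outcome (Aim 1) and 0.05 across the 3 secondary outcomes (2 temperatures, cognitive function"; it continues "such that the secondary outcomes will be assessed at a significance criterion of" 0.05/3 = 0.017. The Sample Size Justification uses the same fixed threshold ("For the 3 secondary outcomes each using a significance criterion of" 0.05/3 = 0.017) and states that "we would have 90% power to detect an effect size of 0.76".

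The number of surgeons comes from the primary outcome alone: "we would need a total of 26 subjects to have 90% power". No step-down, hierarchical or gatekeeping rule appears anywhere, and no confidence intervals are specified for the secondary outcomes. The Methods section promises a full statistical analysis plan before data are looked at, so there is still a natural place to refine the rule.

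**The concern.** Under the plan, each secondary outcome must reach 0.05/3 however convincing the other two are. If both temperature outcomes are clearly significant, cognition is still judged at 0.017. The hypothesis in the Introduction is that the vest lowers body temperature and also preserves cognition, so several effects are expected together. That is the situation in which a fixed Bonferroni threshold gives up most power relative to a step-down test at the same familywise limit. Because the primary outcome determines the sample size, secondary power could otherwise be raised only by adding surgeons, each contributing four operations.

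**Working it through.** **Inputs.** From the Data Analysis section: familywise 0.05 over three secondary outcomes, 0.05/3 each. From the Sample Size Justification: 26 surgeons, difference 2, SD 3 per condition, within-subject correlation 0.5, secondary effect size 0.76 at 90% power. Assumed, because the documents do not say: two-sided tests, and a correlation of 0 to 0.5 between the secondary outcomes.

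**1. Reproduce the plan's figures.** SD of the difference = √(9 + 9 − 2 × 0.5 × 3 × 3) = 3, so d = 2/3. A two-sided paired t-test at 0.05 (noncentral t, df = n − 1) needs n = 26, with power 90.4%. A one-sided test would need 21, which supports the two-sided reading. At n = 26 and α = 0.05/3, the effect detectable with 90% power is 0.766, and power at 0.76 is 89.5%. The plan's 26 and 0.76 therefore stand.

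**2. Error control.** Bonferroni: 3 × 0.05/3 = 0.05. Holm: suppose m of the three null hypotheses are true. The first time a true null is rejected, at least m hypotheses are still in play, so its p-value is at most 0.05/m. The chance that any of m true nulls falls that low is at most m × 0.05/m = 0.05, whatever the dependence. Each Holm threshold is at least 0.05/3, so Holm rejects whatever Bonferroni rejects.

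**3. Power on the plan's scale.** Single-test power at n = 26:

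| Effect | α = 0.05/3 | α = 0.05/2 | α = 0.05 |
|---|---|---|---|
| 0.76 | 89.5% | 92.4% | 96.1% |
| 0.50 | 50.4% | 57.1% | 68.8% |

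Simulation of the full procedures (200,000 trials per scenario, one paired difference per surgeon; ranges are for correlations 0 and 0.5):

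| True effects | Quantity | Bonferroni | Holm |
|---|---|---|---|
| 0.76, 0.76, 0.76 | each outcome | about 90% | 94-96% |
| 0.76, 0.76, 0.76 | all three | 72-77% | 88-90% |
| 0.76, 0.76, 0.50 | third outcome | 50% | 67% |
| 0.76, 0.76, 0 | each real outcome | about 90% | about 92% |
| 0.76, 0.76, 0 | false claim on third | about 1.6% | about 4.5% |
| 0.76, 0, 0 | real outcome | 89.6% | 89.7% |
| 0, 0, 0 | any false claim | 4.5-4.9% | 4.5-4.9% |

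In every scenario the chance of at least one rejection was identical under the two rules, and Holm lost no Bonferroni rejection.

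**4. Allow for two cases per arm.** The Protocol section has each surgeon operate twice with the vest and twice without, and the analysis is a mixed model with a random subject effect. With only a random intercept and no variation in treatment effect between surgeons, averaging two cases per arm divides the SD of the difference by √2. Standardised effects are then multiplied by √2: 0.76 becomes 1.07 and 0.50 becomes 0.71. Then:

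- All three at 0.76: per-outcome power is already about 99.7% under Bonferroni. Power for all three goes from about 99% to about 99.9%, a gain of less than 1 percentage point.
- Third outcome at 0.50, others at 0.76: about 84% becomes about 93%.

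If the treatment effect varies between surgeons, the gain lies between steps 3 and 4.

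**The case against.** The strongest reply is that nothing is wrong with the plan. The 0.05/3 rule is valid, prespecified and applied consistently in both sections, and keeping it biases nothing. That is accepted: a reader might infer an error or inflated false-positive risk, and the documents support neither.

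Three further objections limit the claim.

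- **Holm is not free.** Both rules share the 0.05 ceiling, but Bonferroni's realised error is lower when some effects are real. With both temperatures real at 0.76 and cognition truly null, a false cognition claim goes from about 1.6% to 4.5%. A sponsor could defend wanting the stricter threshold. Simultaneous confidence intervals that match a step-down test are also less direct, although the plan specifies none.
- **The larger gains depend on the scenario and the model.** The 0.76 is a detectable effect, not an expected one, and 0.50 is an assumption of this review. With only one real effect Holm adds almost nothing. The one-difference-per-surgeon model ignores the replication within arms. The plan also states separate secondary hypotheses, so success on all three is not itself an objective.
- **Cognition need not be the weakest outcome.** It is tempting to say that cognition is the outcome Holm would rescue. Nothing in the documents ranks the expected effects, so the unequal-effects example is illustrative only.

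Finally, the family itself is unsettled. Specific Aim 2 in the Data Analysis section tests core, mean skin and mean body temperature while the alpha statement counts two temperatures, and exertion and fatigue are tested with no allotted alpha. This is a separate matter. Holm works for any family size, but the gains shown here are for three outcomes.

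What survives is that, at the familywise limit the sponsor itself chose, Holm is never less powerful and needs no added assumption, ordering of outcomes or surgeon.

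**Conclusion.** A worthwhile, low-cost improvement and not the correction of an error. On the plan's own effect-size scale the gain is about 5 or 6 percentage points per outcome when all three effects are 0.76, and up to 17 points (50% to 67%) for a third outcome at an assumed 0.50. Under a random-intercept model with two cases per arm, that third-outcome gain falls to about 9 points (84% to 93%), and the gain for all three at 0.76 almost vanishes. There is a benefit only if at least two effects are real. The conclusion that Holm is never less powerful at the same limit rests on no modelling assumption. The sizes rest on two-sided tests, 26 surgeons and the assumed correlations of 0 to 0.5.

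**What to change.** Before any data are evaluated, replace the fixed criterion in the Data Analysis section with a sentence such as: *The three secondary outcomes will be tested by Holm's step-down procedure at familywise 0.05, comparing the ordered p-values with 0.05/3, 0.05/2 and 0.05 and stopping at the first that fails.* If the family is redefined, use k in place of 3, so that the steps are 0.05/k, 0.05/(k − 1), and so on to 0.05. In the Sample Size Justification, keep 0.76 and describe it as the figure for the first, most stringent step.

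The cost is one sentence and no extra surgeons. The sponsor should accept knowingly the higher realised error for a truly null outcome, still within 0.05. If intervals are added, ordinary or 98.3% intervals (1 − 0.05/3) can be reported, with a note that they need not match the step-down decisions exactly.
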